14.9 Vulvovaginal Samples for KOH and Fungal Culture

At Screening, a vulvovaginal specimen will be obtained for direct microscopic examination with 10% KOH. Subjects must have a positive KOH test at Screening to be randomized to one of the study treatment groups. The Screening KOH will be assessed at the site by the investigator or designee. A vaginal sample will also be obtained at Screening for fungal culture and species identification by the central laboratory and for susceptibility testing against SCY-078, fluconazole and additional antifungal agents. Central susceptibility testing will be done as per CLSI M27-A3 guidelines. An additional vulvovaginal specimen will be collected at the TOC and FU visits for local KOH testing and for fungal culture by the central laboratory for treatment outcome assessment. In addition, susceptibility testing will be done at the central laboratory for all positive cultures for *Candida* spp. Vulvovaginal samples may also be taken at unscheduled visits, if needed.

14.10 Rating of Vulvovaginal Signs by the Investigator Using the VSS Scale

The investigator (or qualified designee) will perform vulvovaginal examinations to rate the subject's signs of infection at the Screening, TOC and FU visits, as well as at unscheduled visits. Investigators will assess the signs of infection using the VSS Scale provided in [Section 21.0 \[Appendix B\]](#), a standardized, predefined scale, where each sign of the vagina and/or vulva will be given a numerical rating based on severity, as follows:

- Edema: absent = 0; mild = 1; moderate = 2; severe = 3
- Erythema: absent = 0; mild = 1; moderate = 2; severe = 3
- Excoriation or fissures: absent = 0; mild = 1; moderate = 2; severe = 3

Other findings will be recorded using the most relevant medical term in the abbreviated physical examination page of the eCRF.

14.11 Rating of Vulvovaginal Symptoms by the Subject Using the VSS Scale

Subjects will be asked to rate their vulvovaginal symptoms at Screening, from Day 1 through the TOC visit (Day 10), at the FU visit and at any unscheduled visit.

Subjects will rate their symptoms of infection using the VSS Scale (see [Appendix B](#)), where each vulvovaginal symptom will be given a numerical rating based on severity, as follows:

- Itching: absent = 0; mild = 1; moderate = 2; severe = 3
- Burning: absent = 0; mild = 1; moderate = 2; severe = 3
- Irritation: absent = 0; mild = 1; moderate = 2; severe = 3

From Day 1 through the TOC visit, subjects will rate their symptoms and record their scores on the VSS Scale included in their subject diaries.

14.12 Randomization

At Baseline (Day 1), subjects who meet all of the inclusion and none of the exclusion criteria will be randomized to one of the six study treatment groups. Subject randomization will be performed using an IWRS, which will assign a unique randomization number for each randomized subject corresponding to a study treatment. Only one randomization number and study drug treatment will be assigned to each eligible subject.

14.13 Study Drug and Subject Diary Dispensing

At Baseline (Day 1), subjects will be dispensed bottles containing study medication (see [Section 12.3.2](#)) and a subject diary that they will complete daily from Day 1 through the TOC (Day 10) visit.

14.14 Study Drug Dosing

Study drug doses will be self-administered by the subjects from Baseline (Day 1) through Day 3. Details of study treatment groups and dietary requirements for treatment administration are provided in [Section 12.1](#) and [Section 12.2](#), respectively.

14.15 Subject Diary Completion

Subjects will complete their diaries from Day 1 through the TOC visit. The subject diaries will include the VSS Scale so that subjects can rate their vulvovaginal symptoms. Subjects will record the date of study medication dosing, daily vulvovaginal symptoms, other medical concerns or complaints and concomitant medications used. Subjects will be instructed to return their subject diaries at the TOC visit (Day 10).

After the TOC visit, subjects will not be required to complete a diary but will be instructed to call the site immediately if they experience new or worsening signs/symptoms or medical concerns/complaints. The site will also determine if any signs/symptoms or other medical concerns/complaints recorded on the diary should be reported as AEs. The information from the subject diary will be included as part of the eCRFs.

14.16 Treatment Compliance Evaluation and Study Drug Collection

Treatment compliance will be reviewed by the investigator or designee at the Day 3 and TOC (Day 10) visits. PK subjects who have completed study drug dosing at the time of their Day 3 visit may have study drug collected on Day 3. Study drug will be collected at the TOC (Day 10) visit for all other subjects. (see [Section 12.5](#) for further details).

Subjects will be instructed to bring all bottles (including empty bottles) of study medication with them at these visits to assess medication compliance. Further details are available in [Section 12.5](#).

14.17 Subject Diary Collection and Review

Subject diaries will be collected and reviewed at the TOC visit.

14.18 Pharmacokinetic Sample Collection

Blood samples for PK analysis will be drawn on Day 3 and Day 10 (± 2) from the PK Subset only, which will consist of 10 subjects per treatment group (total of 60 subjects). On Day 3, samples will be collected at pre-dose (immediately before dosing) and at 2-6 hours' post-dose of either the morning or evening dose. On Day 10, a single PK sample will be collected. For the PK Subset, the Day 10 (TOC) visit must occur as close to Day 10 as possible. This sample may be collected at any time of the day.

On PK sampling days, the investigator must record the dosing times and sample collection times on the eCRF and on the subject's medical record. Procedures for collecting, storing and shipping plasma samples for PK will be described in the PK Manual.

14.19 Vital Signs

Vital signs, including blood pressure (systolic and diastolic), heart rate, respiratory rate and body temperature will be measured at the Screening and TOC visits, as well as at unscheduled visits, if needed.

14.20 Prior and Concomitant Medication Review

All medications (including prescription and over-the-counter medications, supplements and herbal products) taken from 28 days before Baseline (Day1) and through the TOC visit will be recorded on the eCRF. Only the use of antifungal medications, antibiotics for any reason or any other medication to treat an AE will be recorded after the TOC visit through the last study visit (FU). Start and stop dates of concomitant medications taken during antifungal therapy will be recorded on the eCRF. Prior and concomitant medications will be reviewed and recorded at all study visits.

See [Section 13.0](#) for prohibited medications, medications to be administered with caution and further details for non-study treatments.

14.21 Adverse Event Monitoring

AEs will be recorded and reviewed at all scheduled on-site and phone-contact visits, as well as at all unscheduled study visits, from the time the ICF is signed. See [Section 16.0](#) for further reference.

15.0 Study Schedule

Detailed schedules of all study visits and procedures are presented in Schedule of Visits and Procedures (Table 2).

Table 2: Schedule of Visits and Procedures (Study SCY-078-204)

Visit	V1	V2	V3		V4	V5	Unscheduled Visits
	Screening ^a	Baseline ^a	On-site (for PK subset only)	Phone contact (for non-PK subjects)	TOC	Follow-up	
Day (allowable window)	D-1 (-2)	D1	D3	D3 (+3)	D10 (±2)	D25 (+4)	
Study Procedures							
Informed consent	X						
Assignment of Subject ID number	X						
Inclusion/exclusion criteria	X	X					
Medical history and demographics	X						
Abbreviated physical exam	X				X		
Urine pregnancy test ^b	X						If needed
Safety labs ^c	X				X		If needed
Vulvovaginal sample for other pathogens ^d and pH	X						If needed
Vulvovaginal sample for KOH ^e	X				X	X	If needed
Vulvovaginal sample for fungal culture ^e	X				X	X	If needed
Rating of vulvovaginal signs by the investigator	X				X	X	X
Rating of vulvovaginal symptoms by the subject	X	X-----X			X	X	X
Randomization		X					
Study drug and subject diary dispensing		X					
Study drug dosing		X-----X					
Subject diary completion		X-----X					

Visit	V1 Screening ^a	V2 Baseline ^a	V3		V4 TOC	V5 Follow-up	Unscheduled Visits
			On-site (for PK subset only)	Phone contact (for non-PK subjects)			
Day (allowable window)	D-1 (-2)	D1	D3	D3 (+3)	D10 (±2)	D25 (+4)	
Study Procedures							
Treatment compliance evaluation and study drug collection			X ^g	X ^f	X		
Subject diary collection					X		
PK sample collection ^g			X		X		
Vital signs	X				X		If needed
Prior & concomitant medication review	X	X	X	X	X	X	X
AE monitoring	X	X	X	X	X	X	X

Abbreviations: AE=adverse event; D=day; EOT=end of treatment; PK=pharmacokinetic; TOC=test of cure; V=visit

- a. The Screening and Baseline visits may be combined.
- b. Results will be reviewed at Baseline (Day 1) before starting/dispersing study drug .
- c. Hematology and blood chemistry. Laboratory safety testing will be performed by a qualified central laboratory at Screening, TOC visit and at unscheduled visits if needed.
- d. Analysis of samples for other pathogens will be done by a qualified laboratory and will include causative agents for bacterial vaginosis and *Trichomonas vaginalis*. Analysis of samples for other pathogens such as *Chlamydia trachomatis*, *Neisseria gonorrhoeae* or *Herpes simplex* may be performed if suspected.
- e. Vaginal samples for KOH testing will be assessed locally; vaginal samples for fungal cultures, species identification and susceptibility will assessed by the central laboratory.
- f. Treatment compliance will be reviewed at the Day 3 and TOC (Day 10) visits. PK subjects who have completed study drug dosing at the time of their Day 3 visit may have study drug collected on Day 3. Study drug will be collected at the TOC (Day 10) visit for all other subjects.
- g. Blood samples for PK analysis will be drawn on Day 3 and Day 10 (±2) from the PK Subset only (10 subjects per treatment group [total of 60 subjects]). On Day 3, samples will be collected pre-dose (immediately before dosing) and at 2-6 hours' post-dose of either the morning or evening dose. On Day 10, a single PK sample will be collected. For the PK Subset, the Day 10 (TOC) visit must occur as close to Day 10 as possible. This sample may be collected at any time.

16.0 Safety Assessments and Monitoring

16.1 Definition of an Adverse Event

An AE is any untoward medical occurrence associated with the use of a drug in humans, whether or not considered drug related. An AE can therefore be any unfavorable and unintended sign (including an abnormal laboratory finding), symptom or disease temporally associated with the use of a study drug/study intervention, whether or not related to the study drug/study intervention.

Any laboratory abnormality that is deemed to be clinically significant in the opinion of the investigator will be considered an AE and should be recorded in the eCRF, whether or not it is related to the study drug.

Stable chronic conditions that are present prior to clinical trial enrollment and do not worsen are not considered AEs and will be accounted for in the subject's medical history.

The following can be considered AEs:

- An exacerbation of a pre-existing illness
- An increase in frequency or intensity of a pre-existing episodic event or condition
- A condition detected or diagnosed after the initiation of treatment with study medication, even though it may have been present prior to the start of the study
- Continuous persistent disease or symptoms present at Baseline that worsen after signing the informed consent or following the initiation of treatment with study medication

The following are **not** considered AEs:

- Medical or surgical procedures (e.g., surgery, endoscopy, tooth extraction or transfusion); the condition that leads to the procedure is an AE
- Pre-existing disease or conditions present or detected at the start of the study that do not worsen
- Situations where an untoward medical occurrence has not occurred (e.g., hospitalizations for cosmetic surgery or elective surgery or social/convenience admissions)

- The disease being studied or signs or symptoms associated with the disease, unless more severe than expected for the subject's condition or a worsening of the disease being studied

16.2 Definition of a Serious Adverse Event

A SAE is defined as an AE meeting one of the following outcomes:

- Death
- Life-threatening event
- Inpatient hospitalization or prolongation of existing hospitalization
- Persistent or significant disability/incapacity or substantial disruption of the ability to conduct normal life functions
- Congenital anomaly or birth defect

Any other important medical event that may not result in one of the above outcomes may be considered a SAE when, based upon appropriate medical judgment, the event may jeopardize the participant and may require medical or surgical intervention to prevent one of the outcomes listed above.

A life-threatening AE is any AE that places the subject, in the view of the investigator, at immediate risk of death from the AE as it occurred. It does not include an AE that, had it occurred in a more severe form, might have caused death.

16.3 Events of Clinical Interest

The following are considered events of clinical interest (ECIs) if they occur after dosing, and must be reported by the site when it becomes aware of the ECI:

- ALT or AST > 8 x the upper limit of normal (ULN), confirmed by repeat testing
- ALT or AST > 5 x ULN for more than 2 weeks if new compared to Baseline, confirmed by repeat testing
- ALT or AST > 3 x ULN **and** either total bilirubin >2 x ULN or international normalized ratio (INR) >1.5 if new compared to Baseline, confirmed by repeat testing
- ALT or AST > 3 x ULN, confirmed by repeat test, with the appearance of fatigue, nausea, vomiting, right upper quadrant pain or tenderness, fever, rash, and/or eosinophilia (> 5%)

16.4 Overdose

This refers to the administration of a quantity of a medicinal product given per administration or cumulatively, which is above the maximum recommended dose according to the authorized product information.

An overdose can occur if a subject has taken, accidentally or intentionally, a drug administered in a dose exceeding the protocol-specified dose. An overdose must be reported within 24 hours of the site becoming aware of the overdose if such overdose occurs with an associated SAE. If an overdose occurs without an associated SAE, the overdose must be reported within 5 working days and documented in the subject diary and in the subject medical record.

16.5 Pregnancy

Female subjects who become pregnant should be immediately discontinued from the study and followed up to determine the outcome of the pregnancy. The pregnancy must be reported to the Sponsor within 24 hours of the site becoming aware of the pregnancy. If the pregnancy ends for any reason before the anticipated date, the investigator should notify the Sponsor. At the completion of the pregnancy, the investigator will document the outcome of the pregnancy. If the outcome of the pregnancy meets the criteria for immediate classification as an SAE (i.e., postpartum complication, spontaneous abortion, stillbirth, neonatal death or congenital anomaly), the investigator should follow the procedures for reporting an SAE.

16.6 Unexpected Adverse Event

An AE is considered "unexpected" if it is not listed in the IB or is of greater specificity or severity than those that have been observed with the particular study drug being tested. For example, under this definition, hepatic necrosis would be unexpected (by virtue of greater severity) if the IB referred only to elevated hepatic enzymes or hepatitis. Similarly, cerebral thromboembolism and cerebral vasculitis would be unexpected (by virtue of greater specificity) if the IB listed only cerebral vascular accidents. "Unexpected," as used in this definition, also refers to AEs that are mentioned in the IB as occurring with a class of drugs or as anticipated from the pharmacological properties of the drug but are not specifically mentioned as occurring with the particular drug under investigation.

16.7 Grading of Adverse Events

The severity (or intensity) of an AE refers to the extent to which it affects the subject's daily activities and will be classified by the investigator as mild, moderate or severe using the following criteria:

- Mild: Awareness of sign or symptom, but easily tolerated. Not likely to require medical attention.
- Moderate: Discomfort enough to cause some interference with daily activity. May require medical intervention.
- Severe: Intense enough to disrupt daily activities. Likely requires medical intervention.

Clarification of the difference in meaning between “severe” and “serious”

The term “severe” is often used to describe the intensity (severity) of a specific event (as in mild, moderate or severe myocardial infarction); the event itself, however, may be of relatively minor medical significance (such as severe headache). This is not the same as “serious”, which is based on the outcome or action criteria usually associated with events that pose a threat to life or functioning. Seriousness (not severity) serves as a guide for defining regulatory reporting obligations.

16.8 Causality Assessment

The investigator will assess causality (i.e., whether there is a reasonable possibility that the study drug caused the event) for all AEs and SAEs. The relationship will be characterized using the following classification:

- Related: The temporal relationship of the AE with the study drug makes causality possible and as likely or more likely than due to another cause such as other drugs, a surgical intervention or an underlying disease.
- Not related: The temporal relationship of the AE with the study drug makes causality improbable and can be due to another cause such as other drugs, a surgical intervention or an underlying disease.

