16.10 Serious Adverse Event Reporting Requirements

All SAEs must be reported within 24 hours of the site becoming aware of the SAE. Any event that is serious, study drug-related, and unexpected as assessed by the medical monitor or the Sponsor will be submitted to the regulatory authorities in accordance with national regulatory laws and regulations. The PI will be responsible for reporting all SAEs that require reporting to the local or central Institutional Review Board/Ethics Committee (IRB/EC) in accordance with its regulations and guidelines.

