18.8.2 Analyses

Safety analyses will be conducted using the safety population.

AEs will be coded using the Medical Dictionary for Regulatory Activities (MedDRA) Version 19.1 or higher. The incidence and severity of treatment-emergent AEs and SAEs and their relationship to treatment will be summarized by system organ class and preferred term. The percentage of subjects who discontinued study treatment and the reasons for discontinuation will be summarized by treatment group.

Safety laboratory evaluations and vital signs will be summarized as observed values and as changes from baseline. In addition, shifts (with respect to the reference range) from baseline will be presented by treatment group for laboratory tests.

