11.10.1 Adverse Events

AE terms will be coded using MedDRA dictionary. A treatment-emergent AE (TEAE) is defined as an AE that starts or worsen on or after the date of the first dose of study medication. If relationship to treatment is missing, the event will be conservatively considered as being related to study drug. If severity is missing, a separate category of missing severity will be included in the summary table, and no imputation of severity will be performed. Through the data cleaning process, all attempts will be made to avoid missing values for relationship and severity.

All AEs will be presented in a by-treatment and by-subject listing, detailing the verbatim term given by the investigator, the preferred term (PT), system organ class (SOC), onset date, end date, severity, outcome, relationship to study drug, action taken with study drug, other action taken, seriousness and criteria for seriousness. Serious AEs (SAEs) and TEAEs leading to study discontinuation will also be presented in a separate listing.

An overall summary of AEs will be presented by treatment and overall. The summary will include the total number of events, frequency counts and percentages with:

- Any AE
- Any TEAE
- Any serious TEAE
- Any treatment-related TEAE, including definitely related, probably related, and possibly related
- Any TEAE leading to study drug discontinuation

Summaries of the incidence of TEAEs will be displayed by treatment according to the following:

- All TEAEs by SOC in alphabetical order and PT in descending order of frequency (the combined frequency in the two active treatments)
- All TEAEs by SOC, PT, and maximum severity (mild, moderate, or severe)
- All TEAEs by SOC, PT, and maximum causality (not related, related) to the study drug

At each level of summarization, a subject will be counted once if he/she reported one or more events. The severity of TEAEs and relationship to study drug will be summarized in a similar manner. For summaries of relationship to study drug, a subject will be classified according to the closest relationship. For summaries of TEAE severity, a subject will be classified according to the highest severity.

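### Protocol 16.8 leaves no valid causality category for an event that is reasonably possible but likelier due to another cause, so related-TEAE summaries can be undercounted or inconsistent between sites

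*Protocol*

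**What the plan says.** Protocol 16.8 has the investigator judge every AE and SAE for causality, framed as "whether there is a reasonable possibility that the study drug caused the event". Two categories follow:

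- **Related:** the temporal relationship "makes causality possible and as likely or more likely than due to another cause".
- **Not related:** the temporal relationship "makes causality improbable and can be due to another cause".

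There is no third category and no rule for intermediate cases.

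The classification feeds the safety tables. Protocol 18.8.2 states: "The incidence and severity of treatment-emergent AEs and SAEs and their relationship to treatment will be summarized". SAP 11.10.1 uses relatedness in two places. The overview table has the row "Any treatment-related TEAE, including definitely related, probably related, and possibly related", and the detailed table is "All TEAEs by SOC, PT, and maximum causality (not related, related) to the study drug". The SAP also has a rule for blanks: "If relationship to treatment is missing, the event will be conservatively considered as being related to study drug".

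**The concern.** The question in 16.8 and its answer categories set different thresholds. The question asks only for a reasonable possibility. Related asks for at least equal likelihood against the alternatives, and Not related asks for improbability. The interval between them is not covered.

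Such events are easy to imagine in this trial. Protocol 7.1 names mild gastrointestinal events (nausea, vomiting, diarrhea, abdominal pain) as the most frequent AEs after oral dosing, and these often have a competing explanation.

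At stake is how far the related-TEAE summaries can be read across regimens. Safety and tolerability of the dose levels and regimens is a secondary objective (Protocol 8.2). With small groups, a few coding decisions can change how a regimen looks.

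**Working it through.** **Step 1. Set the definitions side by side (Protocol 16.8).**

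| Event | Reasonable possibility? | Meets Related? | Meets Not related? |
|---|---|---|---|
| Causality possible, at least as likely as another cause | Yes | Yes | No |
| Causality possible and not improbable, but another cause likelier | Yes | No | No |
| Causality improbable, another cause available | No | No | Yes |

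The middle row has no category. It is also where the Related definition disagrees with the governing question.

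**Step 2. Follow a middle-row event into the tables (SAP 11.10.1).**

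- Coded Not related: it drops out of the related count.
- Coded Related, by an investigator who follows the opening question: it is counted.
- Left blank: it is counted as related under the missing-relationship rule.

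So the count can be too low, but the documents do not settle which path sites will take.

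**Step 3. Check whether the SAP grades change a count.** The overview row pools the three grades and they are not tabulated separately. The SOC/PT table uses the protocol's two categories. With a two-level variable, the pooled row is simply the Related count, so the label mismatch alone changes no number.

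**Step 4. Scale.** The documents give no related-event rate, so there is no figure to reproduce. The only documented inputs are 30 subjects per group, about 180 in total (Protocol 10.1), and approximately 20 centers (Protocol 10.4).

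- One subject in a group: 1/30 = 3.3 percentage points.
- Average enrolment per center: 180/20 = 9 subjects, or 9/6 = 1.5 per treatment group. Randomization is unstratified (Protocol 10.2), so differences in site coding habits balance across groups only by chance.

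For illustration, let p be the assumed share of subjects with a reasonably possible drug-related event. Let g be the assumed share of those subjects who end up classified Not related because of the gap. The expected number of related subjects is 30 × p × (1 − g):

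| p (assumed) | g = 0 | g = 10% | g = 25% | g = 50% |
|---|---|---|---|---|
| 5% | 1.5 | 1.35 | 1.13 | 0.75 |
| 10% | 3.0 | 2.7 | 2.25 | 1.5 |
| 30% | 9.0 | 8.1 | 6.75 | 4.5 |

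The chance of seeing at least one related subject in a group is 1 − (1 − p(1 − g))^30. At p = 5% it falls from 0.785 to 0.749, 0.682 and 0.532 across the same values of g.

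The loss in a group's related rate is p × g. Over this grid it runs from 5% × 10% = 0.5 points to 30% × 50% = 15 points. A range that wide shows the size is not determined by anything in the documents.

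**The case against.** **The wording can be read as complete.** If *improbable* means only less probable than the alternative, every event has a category. But Not related would then include events with a reasonable possibility of causation, which contradicts the question the section asks. On the strict reading there is a gap; on the loose one there is a contradiction. The text needs repair either way.

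**The effect on the trial is limited.** This largely stands. TEAEs are tabulated by SOC and PT and by severity regardless of causality, and every AE is listed with its relationship (SAP 11.10.1). The related rate is one safety summary among several, in an exploratory study not powered for formal comparisons (Protocol 18.0, 18.1). A subject is classified by her closest relationship, so one who has another Related event does not move.

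**Sites are blinded (Protocol 10.2), so miscoding should be similar across groups.** This is a fair answer to a charge of bias towards one regimen. It does not restore the level, and an equal proportional loss shrinks differences. With assumed true rates of 30% and 10% and g = 25%, the rates become 22.5% and 7.5%, and the difference falls from 20 to 15 points.

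**Stronger readings a reader might infer, and why they fail:**

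- *That the SAP's grades cause undercounting.* They do not, as Step 3 shows. The same SAP list refers to two active treatments in a six-group trial, which suggests carried-over text.
- *That the protocol's threshold is stricter than the SAP's.* The SAP names a possible grade but never defines it, so there is no SAP threshold to compare.
- *That expedited reporting is compromised.* Protocol 16.12 sends all SAEs to the sponsor within 24 hours whatever their causality. Protocol 16.10 submits to regulators "Any event that is serious, study drug-related, and unexpected as assessed by the medical monitor or the Sponsor". An investigator's Not related does not block the first and, on the text, does not decide the second.

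**Conclusion.** The defect is in Protocol 16.8: two categories that are not exhaustive and do not match the question they are meant to answer. Related-TEAE summaries can be undercounted, or can mix different site conventions.

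A reader might go further and conclude that related events are undercounted, or by how much. The documents support neither. The eCRF is not among them, and a gap event coded Related or left blank is still counted. The 0.5 to 15 point range above rests wholly on assumed p and g, and on gap events being coded Not related. The only scale figure that comes from the plan is 3.3 points per reclassified subject in a group of 30.

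The primary endpoint, the all-cause TEAE tables and SAE reporting to the sponsor are untouched. The SAP label mismatch is a separate tidying matter, although SAP section 12 reports no significant change from the protocol and does not mention it.

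**What to change.** 1. **Protocol 16.8:** define Related as a reasonable possibility that study drug caused the event, and Not related as no reasonable possibility. The two are then exhaustive and answer the section's own question. Drop the comparison with other causes from the definitions.
2. **eCRF completion guidance:** carry the same two definitions.
3. **SAP 11.10.1 (consistency edit, no count changes):** in the overview row, replace the three undefined grades with the collected category Related, so that both causality summaries use the same two levels.

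The cost is wording in three documents. No dose, schedule, sample size or test changes. If events have already been coded when the change is made, those judged under the existing text would need review so that the table does not mix two definitions. The one small downside is that the reported related-TEAE rate may rise slightly.
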